	
Before and after exposure therapy, and before and after each behavioral avoidance test (BAT), participants will additionally self-report on their emotional state (e.g., fear levels) and beliefs (e.g., belief that public speaking practices will be/were harmful/negative). During exposure therapy, participant's physiological responding will be recorded (heart rate and electrodermal skin response). After exposure therapy is complete, participants will fill out a question indicating their best guess as to their treatment assignment (placebo or active tDCS). This question is to ensure that blinding was effective.
 
Behavioral avoidance tests (BATs): Participants will be complete two behavioral avoidance tests. The BATs will involve providing two public speeches to an audience in virtual reality that is A) 75% matched to the participant's ethnicity, and b) 75% un-matched to the participant's ethnicity. Participant's responding will be measured subjectively (with self report items), physiologically (with electrodermal skin response and with heart rate), and behaviorally (recording duration eye contact with audience members, and overall duration of the speech). The subjective, physiological, and behavioral measures of anxiety during the behavioral avoidance task provide a triangulated measurement of the construct of public speaking anxiety. The behavioral approach tests will be completed at baseline and 1-month follow up.
 
Modifications to procedures due to COVID-19 restrictions: For the online follow-up survey, only the following questionnaires will be included, due to participants' completing the survey at home: Intergroup Anxiety Scale, Personal Report of Public Speaking Anxiety, Self-Statements During Public Speaking, and a modified MINI – Social Anxiety interview so that participants can answer the questions without the presence of an interviewer. See Appendix- Questionnaires to view interviews that have been modified to questionnaires.

40. How will researchers analyze the data? ^{xvi}	Primary analyses will be ANCOVAs, evaluating the impact of tDCS group (active vs sham) on outcome measures (questionnaires, physiology, and behavior) at post-treatment and follow-up, controlling for baseline levels. The hypothesis is that participants with active (vs sham) tDCS will have

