	
Our best estimate of other more minor symptoms comes from a recent publication. Poreisz et al., (2007) tested 102 participants in 567 tDCS sessions. In post-session questionnaires asking for ratings from 1(low) - 5 (high), a mild-tingling sensation occurred in 71% of participants and was given a mean rating of $1.74 \pm .84$. Other effects included moderate fatigue in 35% (rated 2.17 ± 1.11), itching under the electrode placement in 30% (rated $1.6 \pm .72$). More serious symptoms of burning sensations were reported in 22% (rated $1.59 \pm .91$) and pain in 16% (rated $1.41 \pm .71$). However, no participant asked to terminate a session. In our testing experience, participants describe a slight itching sensation when the stimulation begins and ends. We anticipate participants describing slight itching and tingling. If participants report burning and pain at any point during the session, we will ask them if they would like to end the testing session. If the symptoms are not resolved by ending stimulation, we will take the participant to the health center or call medical emergency services if needed. If the participant reports feeling extreme symptoms during stimulation in the 'Post-Study Questionnaire' we will speak with the participant to see if medical attention is needed.
 
3) Additionally, completing procedures such as exposure therapy and the behavioral avoidance tests, can produce an increase in anxiety; during these procedures participants are engaging in a feared task on purpose (in this study, giving a public speech). However, this risk of psychological distress does not exceed what one might experience in daily life (e.g., when asked to provide a speech/presentation in a classroom setting). To provide participants resources for additional social anxiety treatment if desired, all participants who begin treatment will be provided a referral document, listing contacts for local mental health resources, at the end of the study.
 
4) Finally, the use of immersive virtual reality (used to administer exposure therapy in our study) can occasionally lead to transient side effects such as motion sickness, dizziness, or headaches. Following procedures used by prior studies of VR-based exposure therapy for public speaking anxiety (Anderson et al., 2013), we will mitigate the risk of simulator sickness by limiting the virtual reality exposure therapy session to 20-30 minutes. Participants will be allowed to request to stop VR sessions early, or take breaks during VR sessions, as needed if they are experiencing symptoms associated with simulator sickness.
 
Anderson, P. L., Price, M., Edwards, S. M., Obasaju, M. A., Schmertz, S. K., Zimand, E., & Calamaras, M. R. (2013). Virtual reality exposure therapy for social anxiety disorder: A randomized controlled trial. Journal of Consulting and Clinical Psychology, 81(5), 751-760. http://dx.doi.org/10.1037/a0033559
 

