
44. List the discomforts and physical harms that might result from participation in this research; assess the probability, severity, and duration of each discomfort/harm:
	
1) Potential physical discomfort associated with tDCS: There is risk of seizure, skin irritation (itching, tingling, redness, pain) and burning associated with the application of electrical current to the scalp. There is risk of headache and discomfort from the adjustable bands that hold the electrodes in place. Seizure activity is associated with symptoms of attention deficiency, nausea, mood changes, and changes in perception, thus, these symptoms are also monitored. However, there have been no seizures associated with tDCS. Symptoms associated with seizure activity (nausea, mood and perceptual changes) are unlikely. The stimulus parameters we propose (1-2 mA stimulation) are consistent with what has been safely used by other researchers and because of this we think that the likelihood of a serious event is very small.
 
Our best estimate of other more minor symptoms comes from a publication on a large sample exposed to tDCS. Poreisz et al., (2007) tested 102 participants in 567 tDCS sessions. In post-session questionnaires asking for ratings from 1(low) - 5 (high), a mild-tingling sensation occurred in 71% of participants and was given a mean rating of $1.74 \pm .84$. Other effects included moderate fatigue in 35% (rated 2.17 ± 1.11), itching under the electrode placement in 30% (rated $1.6 \pm .72$). More serious symptoms of burning sensations were reported in 22% (rated $1.59 \pm .91$) and pain in 16% (rated $1.41 \pm .71$). However, no participant asked to terminate a session. In our testing experience (in the [name]/co-PI lab), participants typically describe a slight itching sensation when the stimulation begins and ends. Therefore, we anticipate participants will likely describe slight itching and tingling, but that this effect will be transient.
 
(2) Potential simulator sickness related to VR use: Probability of simulator sickness is reported by Gregg & Tarrier (2007): "In a series of experiments 80% of all participants reported an increase in sickness symptoms following immersions in a virtual environment (Cobb et al., 1999). For the majority this was a mild increase, which subsided after exiting the immersion. However, 5% could not complete the immersion because the effects were so aversive. Symptom onset typically occurred within 15 min of starting. In repeated trials, symptoms were worse during the first immersion and were negligible by the third."
 
Thus, it is likely that a participant might experience a mild, but transient, increase in simulator sickness symptoms (e.g., slight nausea, headache, etc), but rare that the increase would be so significant that a participant would need to terminate an exposure therapy session. This risk is further mitigated in the present study due to little to no movement in position during the public speaking simulation.
 

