
47. How will participants be referred to psychological, or other services that may be required as a consequence of participation in the research?
	
 N/A, need for referrals not anticipated
 
Explanation: Participants are unlikely to need psychological referrals as a consequence of participating in the current research. However, participants may have a desire to continue exposure therapy (the dosage of exposure therapy provided in the study less than standard clinical care). Therefore, participants will receive a handout at the end of the study providing them with contact information for mental health resources/clinics in the Reno area.
 
Physical side effects:
 
If the participant feels physically unwell during the session, the session will be halted. It is anticipated that symptoms will cease once the electrodes are removed and when the VR head mounted display is removed. However, in the unlikely occurrence of a seizure,

	
the emergency response team will be contacted immediately. Emergency contact numbers are posted in the lab for easy access. Research staff will contact 911 in the case of any medical emergency.
 
If the participant reports a more minor medical condition - such as the slight tingling associated with tDCS or slight nausea due to VR, we will monitor the condition during the session. The post-Therapy questionnaire will be administered at the end of the treatment/exposure therapy session to monitor physical symptoms. During the Post-Therapy Questionnaire, if a serious side-effect comes to light, we will ask the participant if emergency treatment is needed and we will either take the participant to the health center or call emergency services (911). There will be a first aid kit in the laboratory to provide care for any minor treatments. For example, the participant may request an ice pack to the area under electrodes if the skin is irritated.

--	---

Safety Monitoring for Greater than Minimal Risk Research

Check here if this is minimal risk research and safety monitoring is not required; **skip** to next section.

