
48. Describe the plan to monitor data for safety. Include:
 
 • Who will monitor the data for safety concerns? • What data will be reviewed? • How often will the monitoring occur? • How often will cumulative data be reviewed? 	
After the treatment session, participants will fill out a 'Post-Therapy Questionnaire' to assess how he/she feels along a series of dimensions. These data will provide a formal record demonstrating any after effects of the stimulation. The research staff member running the study procedures will monitor/review this questionnaire each session before the participant leaves. The cumulative data on this will be reviewed upon the final analysis of the study data.

49. Are there specific findings that would trigger an immediate suspension of the research?
	
 No  Yes, specify:

Research Benefits

50. Are individual participants expected to benefit from being in this research?
	
 No  Yes, specify: Participants with fears of public speaking could experience a reduction in these fears as a result of the exposure therapy intervention. It is possible that participants with tDCS augmentation could experience enhanced treatment benefits. Participants will also benefit from compensation via course credits or amazon gift cards.

51. What is the potential value of the knowledge to be gained from this research?
	
Outcomes of this study will shed light on the whether tDCS, a low-risk and cost-effective neuro-stimulation tool, can be used to improve outcomes of exposure therapy for individuals with symptoms of social anxiety.

Protecting Participant Privacy

52. Will Protected Personally Identifiable Information (PPII) be collected for this research (see Policy Manual Definitions)?
	
 No  Yes, specify what PPII will be collected and why it is necessary to collect it:

---	---

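### The one clearly timed side-effect reading comes after two baseline VR tests and the exposure session, with no physical-symptom reading before stimulation, so carry-over cannot be separated from new symptoms in an individual.

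*Combined protocol and SAP*

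**What the plan says.** Two places tie the side-effect form to a definite time. Item 47: "The post-Therapy questionnaire will be administered at the end of the treatment/exposure therapy session to monitor physical symptoms". Item 48: "After the treatment session, participants will fill out a 'Post-Therapy Questionnaire". Item 48 adds that staff will "monitor/review this questionnaire each session before the participant leaves", defers cumulative review to the final analysis, and gives the purpose: "These data will provide a formal record demonstrating any after effects of the stimulation".

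Other places are looser. Item 39 puts a side-effects form, covering both tDCS and VR, after VR and tDCS sessions (plural, no visit named). Item 42 calls the form a Post-Study Questionnaire and expects it to pick up symptoms felt while current was on.

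VR is also used outside the exposure session. Item 39: "The behavioral approach tests will be completed at baseline and 1-month follow up". There are two of these behavioral tests (BATs) at each time, both in VR. The self-reports around each BAT are described as emotional state and beliefs; physical symptoms are not listed.

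Item 44 quotes a source on VR sickness: "In repeated trials, symptoms were worse during the first immersion and were negligible by the third". The same source says that for most people the increase was mild and went away on leaving VR, and that onset was typically within 15 minutes.

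For follow-up during campus closure, item 39 says: "For the online follow-up survey, only the following questionnaires will be included". The list that follows has four instruments, none on side effects.

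**The concern.** Item 44 names headache and nausea in both its tDCS paragraph and its VR paragraph. A participant who ticks either symptom on a single end-of-session form could have arrived with it, developed it in a baseline BAT, developed it in the VR exposure, or developed it from stimulation or the electrode bands. The form gives the same answer in all four cases, yet item 48 presents the result as showing what stimulation did.

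The timing is also poorly matched to the protocol's own account of VR sickness. If symptoms are worse at the first immersion and usually fade on exit, a form given after later immersions is not placed to record them as they happen.

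At stake is the safety description: what can be said about one participant's symptoms, how well VR was tolerated when it was first used, and whether anything began after the participant left visit 1.

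**Working it through.** The plan gives no calculation on this point, so there is no figure to reproduce. The check is one of sequence, with simple arithmetic.

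**1. Order of events at visit 1.** Item 13 places the baseline evaluation at visit 1. Item 36 gives two contacts and a one-visit intervention. Item 39 puts the BATs at baseline and at one month. So the order is two baseline BATs, then exposure with active or sham tDCS, then the form. The documents do not print a visit schedule; this order follows from the word baseline.

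**2. VR before the form.** Inputs: two BATs of at most 5 minutes each and six 3-minute trials (item 28).
- Speeches: 2 + 6 = 8.
- Speaking time: 2×5 + 6×3 = 10 + 18 = 28 minutes at most.
- Share falling before stimulation: 10/28 = 36% at most.

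**3. Which immersion the form follows.** The documents do not say whether the headset comes off between speeches.
- Each BAT counted as one immersion: exposure starts at the third, where the source calls symptoms negligible.
- Both BATs counted as one: exposure is the second.
- Under either count, the first immersion has no form of its own.
- Onset window: 15 − 10 = 5 minutes. Symptoms with typical onset could therefore also begin early in the exposure session, which the form does follow.

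**4. What one reading can and cannot separate.** Let a symptom score at the end be Y = B + C + V + S, where B is present on arrival, C is carried over from the BATs, V arises from VR during exposure, and S arises from stimulation.
- End reading only: Y is seen and none of its parts.
- With a reading after the BATs and before stimulation: B + C is seen, so the change estimates V + S. V and S are still mixed in an individual.
- Active minus sham: B, C and V have the same distribution in both arms, because allocation is randomized and the schedule is the same. They cancel in expectation, leaving the difference in S. The missing reading does not bias this contrast.

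**5. Precision.** For a roughly continuous symptom score, adjusting for a pre-stimulation reading multiplies the variance of the arm difference by 1 − ρ², where ρ is the pre-post correlation. The documents give no ρ, so a range is assumed:
- ρ = 0.3: 1 − 0.09 = 0.91.
- ρ = 0.5: 1 − 0.25 = 0.75.
- ρ = 0.7: 1 − 0.49 = 0.51.

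**6. After visit 1.**
- Closure survey: a closed list of four instruments with no side-effect item.
- In-person visit 2 (two more VR BATs): no form is explicitly scheduled, but the plural in item 39, the each-session wording in item 48 and the Post-Study name in item 42 could be read to include it.

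**The case against.** Four points on the other side stand and limit the conclusion.

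- The form is at least partly retrospective, since item 42 expects it to capture symptoms felt during stimulation. Its recall window is not in the text available. A reader might infer that early VR symptoms are missed altogether; the documents do not show that.
- Safety is watched in real time. Item 47 halts the session for a participant who feels unwell and monitors reported minor symptoms, including slight nausea from VR. Item 42 allows breaks and early stopping. Calling the first immersion unmonitored would be wrong. What is absent is any described recording or grading of these reports, which depend on the participant speaking up.
- Both arms follow the same schedule against sham, so the between-arm contrast is sound. Item 39 also states openly that the form covers VR as well as tDCS.
- The documents expect tDCS sensations to be transient and give no figure for delayed effects, so the follow-up question rests on completeness rather than on a known risk.

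Two further inferences are tempting. One is to apply the source's 80% (any increase) and 5% (could not complete) to the 200 planned participants as expected events. Those rates come from other virtual environments, are not stated for first immersions only, and item 44 argues for lower risk here because participants hardly move. The other is to add BAT time to exposure time and claim a breach of the 20-30 minute limit. Item 42 reads "we will mitigate the risk of simulator sickness by limiting the virtual reality exposure therapy session to 20-30 minutes"; it limits the exposure session, not total VR time, so there is no contradiction.

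**Conclusion.** The point holds in a limited form. There is one clearly timed side-effect reading, after up to 8 VR speeches, and no physical-symptom reading before stimulation is described. The data therefore cannot serve as item 48's record of stimulation after-effects for an individual, and early VR symptoms are recorded neither separately nor at the time.

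The randomized comparison of side effects is unbiased. The loss is in individual attribution, in precision (variance 9% to 49% lower with adjustment if ρ is 0.3 to 0.7, an assumed range for a scored symptom) and in the VR tolerability record.

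For closure follow-up, the absence of a side-effect item is certain. For in-person visit 2, a reader might infer that nothing is collected; the wording supports only that the schedule is unclear.

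The conclusion assumes that the baseline BATs precede stimulation at visit 1. It does not depend on how immersions are counted, provided the BATs and the exposure session are not one unbroken immersion. This is a worthwhile, inexpensive improvement, not a threat to the trial's main result.

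**What to change.** 1. Give the existing side-effects questionnaire after the baseline BATs and before the electrodes are placed, and keep the reading at the end of the treatment session.
2. Report, by arm, symptoms that are new or worse than the pre-stimulation reading. State that such a change still includes VR effects arising during exposure, and that only the active-versus-sham difference isolates stimulation.
3. Add one question on symptoms that began after visit 1 to both the in-person visit 2 and the closure online survey.
4. Reconcile the three names (side effects questionnaire, Post-Therapy Questionnaire, Post-Study Questionnaire) and their timings across items 39, 42, 47 and 48, and say whether the form is given at visit 2.

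The cost is a wording amendment and a few minutes per participant on an existing form. There are two statistical downsides. An earlier form may prime participants to notice symptoms; this should affect both arms alike but could raise overall rates. The one-month question is open to recall error, so its answers should be reported separately from the same-day readings.

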- ix **Add** form *Consent Waivers*.
- x **Disclose** costs to participants or 3rd-party payer in consent materials.
- xi **For example:** Retinal scans, skin galvanometers,
- xii **NOTE:** All research components that are experimental must be identified as such in consent materials.
- xiii **Include** information that will be obtained from existing records, from activities/procedures performed solely for the research, or from activities/procedures performed as part of standard treatment/educational practice.
- xiv **Include** descriptions for obtaining data from existing records, prospectively from study procedures, or prospectively from procedures performed for standard treatment/educational practices.
- xv **Add** non-standard instruments as *Questionnaire/Survey or Data Collection*, as applicable.
- xvi **For multi-site research specify** if site-specific data will be analyzed separately. If data will be pooled, indicate if participant identifiers will be maintained and describe how findings will be shared among cooperating PIs.
- xvii **ONLY** for video or photographs, **Add** video/photo release form. (Release form not required for VA research.)
- xviii **See** [University IT Data Management](#) on the web for information about electronic data management/storage solutions. Additional requirements apply to storage of identifiable information outside of the University. Investigators planning to store identifiable data on a cloud-based solution or off-campus, *must* contact the University Chief Information Security Officer in the University IT office for requirements.
- xix Add copies of the site's privacy/data security policies.
- xx **Add** all consent materials.
- xxi Use either the *Consent Checklist* to revise sponsor consent templates or a *Consent Form Template* from IRBNet to create a consent document.
- xxii **Add** form *Consent Waivers*.
